4.9 Discontinuation of investigational product

An individual patient will not receive any further IP if any of the following occur in the patient in question:

- Withdrawal of consent from further treatment with IP. The patient is, at any time, free to discontinue treatment, without prejudice to further treatment. A patient who discontinues treatment is normally expected to continue to participate in the study unless they specifically withdraw their consent to further participation in any study procedures and assessments (see Section [4.10.2](#)).
- Any AE that meets criteria for discontinuation as defined in the Dosing Modification and Toxicity Management Guidelines (see study-specific information in sub-protocols). Note that this is arm specific; this would not impact enrollment into the other arms in the study.
- Initiation of alternative anticancer therapy including another investigational agent.
- AEs that, in the opinion of the Investigator or the Sponsor, contraindicate further dosing. Note that this is arm specific; this would not impact enrollment into the other arms in the study.
- Confirmed PD per RECIST 1.1 and Investigator determination that the patient is no longer benefiting from treatment with IP.
- Non-compliance with the study protocol that, in the opinion of the Investigator or AstraZeneca, warrants withdrawal from treatment with IP (eg, refusal to adhere to scheduled visits).
- Patients incorrectly initiated on study treatment (eg, patient is determined to have met 1 or more of the exclusion criteria for study participation at study entry and continuing investigational therapy might constitute a safety risk)
- Pregnancy or intent to become pregnant.

Should any of this occur, the patient will not receive any further IP.

If the patient is discontinued from study treatment, the scheduled study visits, data collection, and procedures should continue according to this study protocol until study closure of the arm the patient is participating in. Alternatively, if the patient does not agree to this option, a modified follow-up through methods such as regular telephone contacts or a contact at study closure should be arranged, if agreed to by the patient and in compliance with local data privacy laws/practices (see Section 4.9.2).

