2.4.4.2 Adverse events of special interest for olaparib

Myelodysplastic syndrome/acute myeloid leukaemia

The incidence of MDS/AML in patients treated in clinical trials with olaparib monotherapy, including long-term survival follow-up, was <1.5% and the majority of events had a fatal outcome. All patients had potential contributing factors for the development of MDS/AML, having received previous chemotherapy with platinum agents. Many had also received other DNA damaging treatments. The majority of reports were in germline BRCA mutation carriers and some of the patients had a history of previous cancer or of bone marrow dysplasia. If MDS and/or AML are confirmed while on treatment with olaparib, it is recommended that olaparib should be discontinued and the patient be treated appropriately.

New Primary Malignancies other than MDS/AML

New primary malignancies have been reported in <1% of patients. There were other contributing factors/potential alternative explanations for the development of the new primary malignancy in all cases, including documented BRCA mutation, treatment with radiotherapy and extensive previous chemotherapy including carboplatin, taxanes, anthracyclines and other alkylating and DNA damaging agents.

Pneumonitis

Pneumonitis has been reported in <1.0% patients treated with olaparib monotherapy in clinical studies. Reports of pneumonitis had no consistent clinical pattern and were confounded by a number of pre-disposing factors (cancer and/or metastases in lungs, underlying pulmonary disease, smoking history, and/or previous chemotherapy and radiotherapy). When olaparib was used in clinical studies in combination with other therapies there have been events with a fatal outcome. If patients present with new or worsening respiratory symptoms such as dyspnoea, cough and fever, or an abnormal chest radiologic finding is observed, olaparib treatment should be interrupted and prompt investigation initiated. If pneumonitis is confirmed, olaparib treatment should be discontinued and the patient treated appropriately.

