2.5.2.2 Olaparib

Adverse laboratory findings and/or clinical diagnoses considered to be associated with administration of olaparib monotherapy include haematological effects (anaemia, neutropenia, lymphopenia, thrombocytopenia, MCV elevation and increase in blood creatinine), nausea and vomiting, decreased appetite, diarrhoea, dyspepsia, stomatitis, upper abdominal pain, dysgeusia, fatigue (including asthenia), headache and dizziness. Most of these events were generally mild or moderate in intensity.

In a relatively small number of patients, pneumonitis, MDS/AML and new primary malignancies have been observed. Evidence from across the development programme for olaparib does not support a conclusion that there is a causal relationship between olaparib and these events. These are important potential risks for olaparib and are being kept under close surveillance.

See the latest version of the IB for further information.

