Appendix C Table 8: Management of neutropenia, leukopenia and and thrombocytopenia

Toxicity	Study treatment dose adjustment
CTCAE Grade 1-2	Investigator judgement to continue treatment or if dose interruption, this should be for a maximum of 4 weeks; appropriate supportive treatment and causality investigation
CTCAE Grade 3-4	Dose interruption until recovered to CTCAE grade 1 or better for a maximum of 4 weeks. If repeat CTCAE grade 3-4 occurrence, dose reduce olaparib to 250 mg BID as a first step and 200 mg BID as a second step

8.4.2.3 Management of prolonged haematological toxicities while on study treatment.

If a patient develops prolonged haematological toxicity such as:

- ≥ 2 week interruption/delay in study treatment due to CTC grade 3 or worse anaemia and/or development of blood transfusion dependence
- ≥ 2 week interruption/delay in study treatment due to CTC grade 3 or worse neutropenia ($ANC < 1 \times 10^9/L$)
- ≥ 2 week interruption/delay in study treatment due to CTC grade 3 or worse thrombocytopenia ($Platelets < 50 \times 10^9/L$) and/or development of platelet transfusion dependence

Check weekly differential blood counts including reticulocytes and peripheral blood smear. If any blood parameters remain clinically abnormal after 4 weeks of dose interruption, the patient should be referred to haematologist for further investigations. Bone marrow analysis and/or blood cytogenetic analysis should be considered at this stage according to standard haematological practice. Study treatment should be discontinued if blood counts do not recover to CTC Grade 1 or better within 4 weeks of dose interruption.

Development of a confirmed myelodysplastic syndrome/acute myeloid leukemia or other clonal blood disorder should be reported as an SAE and full reports must be provided by the investigator to AstraZeneca Patient Safety. Olaparib treatment should be discontinued if patient's diagnosis of MDS and/or AML is confirmed.

Further details are provided in the Investigators Brochure.

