8.4.2.4 Management of non-haematological toxicity for ceralasertib and olaparib

Acute toxicities in the all treatment arms should be managed as medically indicated, with temporary suspension of IP and initiation of supportive care as clinically indicated by the treating physician. Treatment must be interrupted if any NCI-CTCAE Grade 3 or 4 non hematologic AE occurs which the Investigator considers to be related to the administration of the study treatment(s). Treatment should not be restarted until the toxicity has resolved to Grade \leq 1.

Repeat dose interruptions are permitted, for a maximum of 28 days. Any patient who develops a Grade 3 or 4 non-haematologic toxicity that does not resolve to \leq Grade 1 within this period, should be removed from the study treatment. Once a dose is reduced, re escalation is not permitted.

A summary of the dose reduction guidance for ceralasertib and olaparib is presented earlier.

At the first occurrence of CTCAE grade 3 and 4 non-haematological toxicity, ceralasertib and olaparib should be held until resolution of toxicity. At the resolution of the first occurrence of any of these toxicities, no change must be made to dose. At the second occurrence, upon resolution of toxicity, ceralasertib and/or olaparib should be reduced by the 1st dose reduction for non-haematological toxicity to 120 mg qd for 7 days and/or olaparib 250 mg BID q 12 hours daily ([Appendix C Table 5](#) and [Appendix C Table 9](#)) Despite this change, at the third occurrence, upon resolution of toxicity, ceralasertib and/or olaparib should be reduced by the 2nd dose reduction to 120 mg qd for 4 days and 200 mg bid q 12 hours daily ([Appendix C Table 5](#) and [Appendix C Table 9](#)). If despite these changes, there is a fourth occurrence of toxicity, the patient should permanently discontinue study drug. Please note that, for each dose reduction, the investigator may choose to reduce ceralasertib or olaparib or both drugs. If only one drug is dose reduced, the second drug may be reduced as an additional step. Refer to [Appendix C Table 9](#) for specific dose modification guidance regarding non-haematological toxicity.

Appendix C Table 9: Summary of guidance on the management of non-haematologic toxicity for ceralasertib and olaparib

Toxicity	Ceralasertib and olaparib

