Any non-haematologic toxicity (CTCAE grade ≥ 3)	
1st occurrence
 
Withhold dose and monitor at least weekly for up to 28 days until recovery to \leqCTCAE grade 1 then resume at original dose level. If a clinical CTCAE give supportive measures and rule out other causes; if a laboratory AE is not resolving within two weeks contact Sponsor for guidance
 
If symptoms do not recover to \leqCTCAE grade 1, contact Sponsor and consider discontinue ceralasertib and olaparib .

	
2nd occurrence
 
Withhold dose for up to 28 days until recovery to \leqCTCAE grade 1 then resume at 1st reduced dose level for non-haematological toxicity (see Appendix C, table 4). The investigator may choose to reduce ceralasertib or olaparib or both drugs. If only one drug is dose reduced, the second drug may be reduced as an additional step if the toxicity recurs.
 
If symptoms do not recover to \leqCTCAE grade 1, contact Sponsor and consider discontinue ceralasertib and olaparib.

	
3rd occurrence
 
Withhold dose for up to 28 days until recovery to \leqCTCAE grade 1 then resume at 2nd reduced dose level for non-haematological toxicity (see Appendix C, table 4). The investigator may choose to reduce ceralasertib or olaparib or both drugs. If only one drug is dose reduced, the second drug may be reduced as an additional step if the toxicity recurs.
 
If symptoms do not recover to \leqCTCAE grade 1, contact Sponsor and consider discontinue ceralasertib and olaparib.

Toxicity	Ceralasertib and olaparib
	4th occurrence
	Off-study drug

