8.4.2.5 Management of new or worsening pulmonary symptoms

If new or worsening pulmonary symptoms (eg, dyspnoea) or radiological abnormality occurs, an interruption in study treatment dosing is recommended and a diagnostic workup (including a high resolution CT scan) should be performed, to exclude pneumonitis. Following investigation, if no evidence of abnormality is observed on CT imaging and symptoms resolve, then study treatment can be restarted, if deemed appropriate by the investigator. If significant pulmonary abnormalities are identified, these need to be discussed with the AstraZeneca Study Physician.

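### Arm C's toxicity table resumes full-dose olaparib after a first recovered Grade 3 or higher event with no exception for pneumonitis, although Appendix C says to stop olaparib once pneumonitis is confirmed

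*Protocol*

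**What the plan says.** Four places in Appendix C and one in the master protocol bear on this.

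- **Section 2.4.4.2 (olaparib adverse events of special interest).** New or worsening respiratory symptoms, or an abnormal chest image, call for interruption and prompt investigation. Then: "If pneumonitis is confirmed, olaparib treatment should be discontinued and the patient treated appropriately". Ceralasertib is not mentioned.
- **Section 8.4.2.4 and Table 9.** The table row reads "Any non-haematologic toxicity (CTCAE grade ≥ 3"), under a column covering both drugs. At a first occurrence, dosing is withheld for up to 28 days until Grade 1 or lower, and the site is to "then resume at original dose level". The text of the section is firmer: "At the resolution of the first occurrence of any of these toxicities, no change must be made to dose".
- **Section 8.4.2.5 (pulmonary symptoms).** It recommends an interruption and a workup with high-resolution CT to exclude pneumonitis. Restart is allowed "if no evidence of abnormality is observed on CT imaging and symptoms resolve, then study treatment can be restarted", subject to the investigator's judgement. Significant abnormalities are to be discussed with the Study Physician.
- **Section 8.4.2.3 (prolonged haematological toxicity).** Olaparib is to be discontinued if the patient's "diagnosis of MDS and/or AML is confirmed".
- **Master protocol Section 4.9.** Dosing stops for "AEs that, in the opinion of the Investigator or the Sponsor, contraindicate further dosing".

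**The concern.** A site managing toxicity works from the dose-modification text, not from the background section. For pneumonitis, the stop instruction is only in the background. The dose-modification text gives a general resume rule that, read literally, includes pneumonitis.

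A patient whose confirmed Grade 3 or higher pneumonitis settled within 28 days would restart olaparib at full dose, against the protocol's own instruction. Section 2.4.4.2 reports fatal outcomes when olaparib was combined with other therapies, and Arm C is a combination arm. Exclusion criterion 7 in Appendix C Section 5.2 also bars patients with previous drug-induced pneumonitis, so Table 9 would re-dose someone who could no longer be enrolled.

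**Working it through.** The main check is a comparison of texts, followed by a short calculation of how often the conflict could arise.

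**Step 1: instruction by situation**

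| Situation | 2.4.4.2 | 8.4.2.4 and Table 9 | 8.4.2.5 |
|---|---|---|---|
| Pulmonary symptoms, CT clear, symptoms resolved | No stop | Not the governing text | Restart allowed |
| Confirmed pneumonitis, Grade 1-2 | Discontinue olaparib | Does not apply (Grade 3 or higher only) | Discuss with the Study Physician if significant; no stop stated |
| Confirmed pneumonitis, Grade 3 or higher, first occurrence, recovered to Grade 1 or lower within 28 days | Discontinue olaparib | Resume both drugs at the original dose | Discuss with the Study Physician if significant; no stop stated |

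Only the third row is a contradiction. In the second row the stop rule is missing from the management text but not contradicted.

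**Step 2: does another section settle it?**

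- Section 8.4.2.5 is consistent with 2.4.4.2, because its only stated route to restart needs a clear CT. It gives no action for confirmed pneumonitis beyond a discussion, does not say what happens to ceralasertib in that case, and claims no precedence over Table 9. Neither section refers to the other, and 8.4.2.4 itself points to Table 9 as the specific guidance for non-haematological toxicity.
- Master Section 4.9 has two relevant routes. One depends on the investigator's or sponsor's opinion. The other depends on criteria in the toxicity management guidance of the sub-protocol, and that is the text from which the pneumonitis stop is absent.
- Section 2.4.4.2 gives olaparib stop rules for both MDS/AML and pneumonitis. The first is carried into Section 8.4.2.3. The second is not carried anywhere in Section 8.4, which suggests an omission rather than a choice.

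**Step 3: how many patients**

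Inputs: pneumonitis incidence below 1% on olaparib monotherapy (2.4.4.2); up to 20 patients planned in Arm C (Appendix C Sections 3 and 9.2); up to 40 if the expansion in the master protocol is used.

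Expected cases of any grade are below n × 0.01:

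- 20 × 0.01 = 0.2
- 40 × 0.01 = 0.4

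The chance of at least one case of any grade is below 1 − 0.99^n:

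- 1 − 0.99^20 = 0.182, about 18%
- 1 − 0.99^40 = 0.331, about 33%

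The contradiction needs a Grade 3 or higher case that recovers in time, so its frequency is lower than these figures. The protocol gives no figure for that subset, and no pneumonitis rate for this combination.

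**The case against.** The strongest reply is that the specific rule governs the general one. Section 8.4.2.5 follows Table 9 directly, and almost any patient with Grade 3 or higher pneumonitis would enter its pathway. Such a patient would not meet its condition for restart. Other organ-specific text in the appendix also departs from Table 9 without stating precedence, for example the renal section (8.4.2.6) and the QTc rule (7.1.3). On this reading, 2.4.4.2 and 8.4.2.5 form one sequence: interrupt, investigate, restart only if clear, discontinue if confirmed. Most investigators would stop in any case. The protocol also notes that the monotherapy reports were confounded and that the evidence does not support a causal relationship.

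Part of this stands. Section 8.4.2.5 does not contradict the stop rule, and a careful reader of the whole appendix would probably reach the right action. No passage requires ceralasertib to stop, so its treatment after confirmed pneumonitis is missing detail and not a contradiction.

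The reply does not remove the defect. The specific-over-general reading has to be inferred, against text in 8.4.2.4 that covers every such toxicity and forbids a dose change. Section 8.4.2.5 is silent on a confirmed case that later recovers, which is the case Table 9 answers with resumption. On causality, the protocol still treats pneumonitis among its safety priorities: "These are important potential risks for olaparib and are being kept under close surveillance".

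**Conclusion.** The concern holds. For a first, confirmed pneumonitis of Grade 3 or higher that recovers to Grade 1 or lower within 28 days, Appendix C gives opposite instructions on olaparib, and nothing in 8.4.2.5 or master Section 4.9 resolves them except by judgement. For Grade 1-2 pneumonitis the stop rule is only missing from the management section.

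The number of patients exposed to the conflict is small. The bounds above assume that the monotherapy incidence applies to the combination, which the protocol does not establish, and they count all grades. The consequence is for the safety of an individual patient. The arm's tolerability summary and the objective response rate are not materially affected. It should be corrected because an error could be serious and the protocol already contains the right rule.

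**What to change.** In Appendix C Section 8.4.2.5, state that confirmed pneumonitis of any grade requires permanent discontinuation of olaparib, and state the action for ceralasertib. In Section 8.4.2.4 and Table 9, except pneumonitis from the resume rule by cross-reference to 8.4.2.5. The ceralasertib action is a decision for the sponsor; the olaparib part only carries Section 2.4.4.2 into the text that sites use.

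The cost is a wording change in these three places. No extra visits, tests or data collection are needed.

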8.4.2.5 Management of new or worsening pulmonary symptoms

If new or worsening pulmonary symptoms (eg, dyspnoea) or radiological abnormality occurs, an interruption in study treatment dosing is recommended and a diagnostic workup (including a high resolution CT scan) should be performed, to exclude pneumonitis. Following investigation, if no evidence of abnormality is observed on CT imaging and symptoms resolve, then study treatment can be restarted, if deemed appropriate by the investigator. If significant pulmonary abnormalities are identified, these need to be discussed with the AstraZeneca Study Physician.

8.4.2.6 Renal Impairment

If subsequent to study entry and while still on study therapy, a patient's estimated CrCl falls below the threshold for study inclusion (≥ 51 ml/min), retesting should be performed promptly. A dose reduction is recommended for patients who develop moderate renal impairment (calculated creatinine clearance by Cockcroft-Gault equation of between 31 and 50 ml/min) for any reason during the course of the study: the dose of olaparib should be reduced to 200mg BID. Because the CrCl determination is only an estimate of renal function, in instances where the CrCl falls to between 31 and 50 mL/min, the investigator should use his or her discretion in determining whether a dose change or discontinuation of therapy is warranted or a more formal test of creatinine clearance determination should be performed.

Olaparib has not been studied in patients with severe renal impairment (creatinine clearance ≤ 30 ml/min) or end-stage renal disease; if patients develop severe impairment or end stage disease it is recommended that olaparib be discontinued.

8.4.2.7 Management of nausea and vomiting

Events of nausea and vomiting are known to be associated with olaparib treatment. They are generally mild to moderate (CTCAE grade 1 or 2) severity, intermittent and manageable on continued treatment. The first onset generally occurs in the first month of treatment with the incidence of nausea and vomiting not showing an increase over the treatment cycles.

No routine prophylactic anti-emetic treatment is required at the start of study treatment, however, patients should receive appropriate anti-emetic treatment at the first onset of nausea or vomiting and as required thereafter, in accordance with local treatment practice guidelines.

8.4.2.8 Interruptions for intercurrent non-toxicity related events

Study treatment dose interruption for conditions other than toxicity resolution should be kept as short as possible. If a patient cannot restart study treatment within 4 weeks for resolution of intercurrent conditions not related to disease progression or toxicity, the case should be discussed with AZ study physician.

All dose reductions and interruptions (including any missed doses), and the reasons for the reductions/interruptions are to be recorded in the eCRF.

Study treatment should be stopped at least 3 days prior to planned surgery. After surgery study treatment can be restarted when the wound has healed. No stoppage of study treatment is required for any biopsy procedure.

Study treatment should be discontinued for a minimum of 3 days before a patient undergoes radiation treatment. Study treatment should be restarted within 4 weeks as long as any bone marrow toxicity has recovered.

Because the AEs related to olaparib may include asthenia, fatigue and dizziness, patients should be advised to use caution while driving or using machinery if these symptoms occur.

9. INVESTIGATIONAL PRODUCT AND OTHER TREATMENTS

9.1 Identity of investigational product(s)

Investigational product	Dosage form and strength
Ceralasertib	20 mg or 100 mg tablets
Olaparib	100 mg or 150 mg film-coated tablets

9.1.1 Ceralasertib

AstraZeneca will supply ceralasertib tablets for oral use. The tablets will be supplied at 2 strengths (20 mg and 100 mg) in high-density polyethylene bottles, which sufficiently protects the drug from light. Ceralasertib coated tablets contain a blend of ceralasertib, mannitol, microcrystalline cellulose, sodium starch glycolate, magnesium stearate and silicon dioxide. The coating is Opadry® II white.

The different tablet strengths should not be combined in the same bottle at any time. Additional information about the IP may be found in the IB.

Ceralasertib is taken PO daily on Days 1 to 7 of each treatment cycle at about the same time each day. Treatment cycles are every 28 days. Ceralasertib should be taken with approximately 8 ounces of water. When ceralasertib is administered in combination with olaparib, patients must fast as directed for at least 2 hours prior to the dosing and for at least 1

hour after the dose. When olaparib is given on its own, the olaparib tablet formulation can be given without regard to food.

If a patient misses a daily dose, a double dose should not be taken on the next day. If vomiting occurs after a patient takes the ceralasertib dose, the patient should not take the dose again unless they can count all of the taken tablets.

